7.3.6. ECOG Performance Status

The performance status will be assessed using the Eastern Cooperative Oncology Group (ECOG) scale ([Appendix 6](#)) as specified in the Time and Events Table (Section [7.1](#)).

7.3.7. Montreal Cognitive Assessment

Montreal Cognitive Assessment (MOCA) was designed as a rapid screening instrument for mild cognitive dysfunction. It assesses different cognitive domains: attention and concentration, executive functions, memory, language, visuoconstructional skills, conceptual thinking, calculations, and orientation. Time to administer the MOCA is approximately 10 minutes.

The test and administration instructions are freely accessible for clinicians at www.MOCAtest.org. English version 7.1 is shown in [Appendix 8](#).

7.3.8. Echocardiogram and/or Multi-gated Acquisition Scans

ECHOs or MUGA scans will be performed at baseline to assess cardiac ejection fraction and cardiac valve morphology for the purpose of study eligibility. Additional ECHO assessments may be performed if clinically warranted. The evaluation of the echocardiographer should include an evaluation for left ventricular ejection fraction (LVEF).

7.3.9. Clinical Safety Laboratory Assessments

All protocol required laboratory assessments, as defined in [Table 4](#) should be performed according to the Time and Events Table (Section [7.1](#)).

Prior to administration of the first dose of study treatment, results of laboratory assessments should be reviewed. Any laboratory test with a value outside the normal range may be repeated (prior to the first dose) at the discretion of the investigator.

All laboratory tests with values that are significantly abnormal during participation in the study or within 14 days after the last dose of study treatment should be repeated until the values return to normal or baseline. If such values do not return to normal within a period judged reasonable by the investigator, the etiology should be identified and the sponsor notified.

Hematology, clinical chemistry, coagulation panel and additional parameters to be tested are listed in [Table 4](#):

Table 4 List of Clinical Laboratory Tests

| Hematology | | | |
|---|--|----------------------------------|---|
| Platelet Count | RBC Indices: | | Automated WBC Differential: |
| Red blood cell (RBC) Count | Mean corpuscular volume (MCV) | | Neutrophils |
| White blood cell (WBC) Count (absolute) | Mean corpuscular hemoglobin (MCH) | | Lymphocytes |
| Reticulocyte Count | Mean corpuscular hemoglobin concentration (MCHC) | | Monocytes |
| Hemoglobin | | | Eosinophils |
| Hematocrit | | | Basophils |
| Blast count | | | |
| Clinical Chemistry | | | |
| Blood urea nitrogen (BUN) | Potassium | Aspartate aminotransferase (AST) | Total and direct bilirubin ¹ |
| Creatinine | Chloride | Alanine aminotransferase (ALT) | Uric Acid |
| Glucose | Total carbon dioxide (CO ₂) | Gamma glutamyl transferase (GGT) | Albumin |
| Sodium | Calcium | Alkaline phosphatase | Total Protein |
| Phosphate | Lactate Dehydrogenase (LDH) | | |
| Other tests | | | |
| Coagulation Panel including aPTT and INR | | | |
| Other screening tests | | | |
| Follicle stimulating hormone (FSH) and estradiol (as needed in women of non-child bearing potential only) | | | |
| Hepatitis B surface antigen (HBsAg) and Hepatitis C antibody (HCV Ab) testing | | | |

1. Direct bilirubin should be assessed only if total bilirubin is elevated beyond the upper limit of normal (ULN)

7.4. Evaluation of Anti-Cancer Activity

Disease assessments will be made by physical examination and laboratory evaluation, which includes a complete blood count with differential. Bone marrow aspiration should be performed if clinically indicated, and to confirm the response. Response criteria are listed in [Appendix 10](#).

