| 1. To evaluate clinical activity after treatment with GSK2879552, alone or in combination with azacitidine, in adult subjects with HR MDS previously treated with HMA. | 1. Clinical benefit rate (CBR) defined as % of subjects achieving CR, mCR, PR, cytogenetic response, HI or SD. Objective response rate (ORR) defined as % of subjects achieving CR, mCR, PR, cytogenetic response, or HI [as per 2006 IWG criteria]). |
| Secondary | |
| 1. To further evaluate the safety and tolerability of GSK2879552 administered alone or in combination with azacitidine. | 1. Changes in safety parameters: e.g. AEs and SAEs, changes in laboratory values, vital signs, electrocardiograms [ECGs], and physical examinations. |
| 2. To characterize the population PK of GSK2879552, alone or in combination with azacitidine in patients with HR MDS previously treated with HMA. | 2. Population PK parameters for GSK2879552 such as clearance (CL/F). |
| 3. To evaluate duration of response, duration of clinical benefit, progression-free survival, and overall survival. | 3. Duration of response (DOR) defined as the time from first documented response to disease progression. Progression free survival (PFS) defined as the time from first dosing day to disease progression or death from any cause. Overall survival (OS) defined as the time from first dosing day until death from any cause. |
| 4. To evaluate frequency and time to progression to AML (per 2006 IWG criteria) | 4. Proportion of subjects with disease progression to AML. Time to AML progression. |
| 5. To evaluate platelet and RBC transfusion dependence. | 5. Number of documented platelet and RBC transfusions per month within 3 months prior to study entry and while on study. |

| Objectives | Endpoints |
|---|--|
| Exploratory | |

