16. Subjects are followed every 2 months to collect the survival, PFS data and the start of new treatment via chart review, or phone call contact. The follow-up will continue until death, lost to follow-up, withdrawal of consent or up to 12 months from end of treatment visit, whichever occurs first.
17. The exploratory BM sample is collected whenever the bone marrow is done for disease assessment and/or at the time of crossover, unless the sample collection is stopped per sponsor discretion; the PK blood sample will be collected pre-dose at the crossover visit if the exploratory BM sample is collected. The PK corresponding blood sample will not be collected if a regularly scheduled PK sample is already being collected during the visit.
18. A mandatory BM sample will be collected at the time of the crossover visit to establish the new baseline. A window of 14 days is allowed for this BM assessment.

Time and Events Table for Arm A – Part 2

| | SC R | Cycle 1 (28 days) | | | | | Cycle 2 and beyond | Crossover Visit | End of Treatment Visit | Post Treatment Bi-monthly Follow-Up ¹⁶ |
|----------------------------------|---------|--|----|-----|------|-----|--|--------------------|------------------------------|--|
| | | D 1 | D4 | D 7 | D 15 | D22 | | | | |
| Office Visit for Arm A (mono) | X | X | X | X | X | X | C2: D1, 7, 15 and 22 C3 and after: D1 | X | X | |
| Informed consent | X | | | | | | | | | |
| Demography | X | | | | | | | | | |
| Medical history | X | | | | | | | | | |
| Disease characteristics | X | | | | | | | | | |
| GSK2879552 Dosing ⁹ | | < ----- Daily or per dosing schedule ----- > | | | | | | | | |
| Azacitidine dosing ¹⁴ | | | | | | | | X ¹⁴ | | |
| Review subject dosing diary | | | | X | X | | Day 1 | X | X | |
| GSK2879552 Drug Dispensing | | X | | | | | Day 1 | | | |
| Complete physical exam | X | | | | | | | X | X | |
| Brief physical exam | | X ⁷ | | X | | | Day 1 | | | |
| Montreal Cognitive Assessment | X | X | | X | X | X | Day 1 | | | |
| ECOG PS | X | X ⁷ | | X | | | Day 1 | X | X | |
| Vital Signs | X | X ⁷ | | X | X | | Day 1 | X | X | |
| Height and weight ⁶ | X | X ⁷ | | X | | | Day 1 | X | X | |
| ECHO/MUGA | X | | | | | | | | | |
| 12-lead ECGs | X | X ⁷ | | X | | | Day 1 | X | X | |
| HIV, HBV and HCV Ab | X | | | | | | | | | |

| | SC R | Cycle 1 (28 days) | | | | | Cycle 2 and beyond | Crossover Visit | End of Treatment Visit | Post Treatment Bi-monthly Follow-Up ¹⁶ | |

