7.6.1. Biomarker Analysis

All subjects will be asked to submit peripheral blood samples at baseline, during the study, and at the end of treatment. All subjects will also be asked to submit fresh bone marrow aspirate at baseline and during the study. There is an optional bone marrow aspirate collection at the end of treatment. These samples will be used to conduct retrospective tests to understand the mechanistic activity of GSK2879552 alone and in combination with azacitidine, therapeutic response and the identification of potential markers of sensitivity or resistance through the assessment of DNA, RNA and/or protein. These studies may include but are not limited to DNA methylation, transcriptomic, and genomic analyses.

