9.4.1. Clinical Activity Analyses

The clinical benefit rate (CBR) is defined as the percentage of subjects with a Complete Remission (CR), marrow complete remission (mCR) or a Partial Remission (PR) or a Hematologic Improvement (HI) or Stable Disease (SD) at any time as per disease-specific criteria ([Appendix 5](#) and [Appendix 6](#)). Subjects with unknown or missing response will be treated as non-responders, i.e. these subjects will be included in the denominator when calculating the percentage. The number and types of responses, as outlined in IWG criteria [[Cheson, 2006](#)], will be listed and summarized separately, as appropriate.

The ORR will be reported at the interim and final analysis for each arm specified in Part 2 as well as all evaluable subjects in Part 1 treated at or above RP2D. Part 1 and Part 2 subjects who received the same dose within the same treatment arm may be combined together in the analysis. The estimates along with 95% exact confidence interval (CI) will be provided.

The CBR and ORR differences between the two cohorts will be provided along with corresponding 95% CI. A chi-square test will be used to test for differences between arms if data warrant.

Duration of response is defined as the subset of subjects who show a response (CR, mCR, PR, or HI), the time from first documented evidence of response until the first documented sign of disease progression or death. Duration of response will be summarized descriptively for each arm, if data warrant, using Kaplan-Meier medians and quartiles. Details on rules for censoring will be provided in the RAP.

For the analysis of **Progression-free survival (PFS)**, if the subject received subsequent anti-cancer therapy prior to the date of documented events, PFS will be censored at the last adequate assessment (e.g. assessment where visit level response is CR, mCR, PR, HI or SD) prior to the initiation of therapy. Progressive disease (PD) will also be defined per standard criteria. Otherwise, if the subject does not have a documented date of events, PFS will be censored at the date of the last adequate assessment. Further details on rules for censoring will be provided in the RAP. PFS will be summarized by arm and dose using Kaplan-Meier quantile estimates along with 2-sided 95% CIs at the time of final analysis, if data warrant.

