12.10. Appendix 10: IWG CRITERIA FOR RESPONSE

| Category | Response Criteria |
|------------------------------|--|
| Complete Remission | Bone marrow: $\leq 5\%$ myeloblasts with normal maturation of all cell linesa Persistent dysplasia will be noteda,b Peripheral blood (Response must be maintained for at least 4 weeks) Hgb ≥ 11 g/dL Platelets ≥ 100 Gi/L Neutrophils ≥ 1.0 Gi/Lb Blasts 0% |
| Partial Remission | All CR criteria if abnormal before treatment except: Bone marrow blasts decreased by $\geq 50\%$ over pre-treatment but still $> 5\%$ Cellularity and morphology not relevant |
| Marrow CR^b | Bone marrow: $\leq 5\%$ myeloblasts and decrease by $\geq 50\%$ over pre-treatment ^b Peripheral blood: if HI responses, they will be noted in addition to marrow CR ^b |
| HI | Erythroid (HI-E): hgb increase of > 1.5 g/dL decrease of $>$ RBC transfusions/8weeks versus pretreatment requirement in previous 8 weeks; only RBC transfusions given for a pretreatment Hgb of < 9.0 g/dL count Platelet (HI-P): increase of $> 30,000$ /mL (starting with $> 20,000$ /mL) increase from $< 20,000$ /mL to $> 20,000$ /mL by $> 100\%$ Neutrophil (HI-N): increase of $> 100\%$ and > 500 /uL |
| Stable Disease | Failure to achieve at least PR, but no evidence of progression > 8 wks |
| Disease Progression | For subjects with: 
 • Less than 5% BM blasts: $\geq 50\%$ increase in blasts to $> 5\%$ blasts • 5%-<10% BM blasts: $\geq 50\%$ increase to $> 10\%$ blasts • 10%-<20% BM blasts: $\geq 50\%$ increase to $> 20\%$ blasts • 20%-30% BM blasts: $\geq 50\%$ increase to $> 30\%$ blasts Any of the following: 
 • At least 50% decrement from maximum remission/response in granulocytes or platelets • Reduction in Hgb by ≥ 2 g/dL • Transfusion dependence |
| Non-evaluable | Subject does not meet any of the above criteria |

BM = bone marrow ; CR = complete remission; Hgb = hemoglobin;; PR = partial remission

a. Dysplastic changes should consider the normal range of dysplastic changes (modification).

b. Modification to IWG response criteria [[Cheson, 2006](#)].

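### Stable disease counts as a primary-endpoint success, but no passage requires a post-baseline marrow before it is assigned, so early blast progression that blood tests miss would be scored as benefit

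*Protocol*

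**What the plan says.** Section 3.2 gives the Part 2 primary endpoint as "Clinical benefit rate (CBR) defined as % of subjects achieving CR, mCR, PR, cytogenetic response, HI or SD". Section 9.4.1 counts the best category reached, "or a Hematologic Improvement (HI) or Stable Disease (SD) at any time as per disease-specific criteria". Under Section 9.1.2 an arm of 28 rejects the null hypothesis with at least 12 responders, and SD also counts at each futility look in Table 5.

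Appendix 10 defines SD as "Failure to achieve at least PR, but no evidence of progression" for more than 8 weeks. It names no marrow result. Its four blast-based progression rules are all stated in marrow blasts, for example the rule for subjects starting at "10%-<20% BM blasts". The other progression rules (falls in granulocytes, platelets or hemoglobin, and transfusion dependence) need no marrow.

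Section 7.4 bases disease assessment on physical examination and laboratory tests, and adds: "Bone marrow aspiration should be performed if clinically indicated, and to confirm the response". All four Time and Events tables in Section 7.1 give disease-assessment marrow at screening, during treatment only when clinically indicated, and optionally at end of treatment. Arm A also has a mandatory marrow at crossover, which happens only after progression.

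Section 7.6.1 reads differently: "All subjects will also be asked to submit fresh bone marrow aspirate at baseline and during the study". Footnote 17 of the tables makes that sample conditional: "The exploratory BM sample is collected whenever the bone marrow is done for disease assessment", or at crossover. Footnotes 11 and 17 also let the sponsor stop it.

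**The concern.** A subject with steady blood counts and no on-treatment marrow has, on the wording of Appendix 10, "no evidence of progression" once 8 weeks have passed. That subject is SD and a CBR success, even if marrow blasts have crossed an Appendix 10 limit unseen.

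Two provisions might be expected to catch the case, and neither does. Section 9.4.1 scores unknown or missing response as non-response, but this subject has a response category. The non-evaluable category in Appendix 10 is for subjects who meet none of the criteria, and this subject meets the criterion for SD.

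What is at stake is how the 12-of-28 result is read. In an open-label trial, part of the success count could depend on whether a marrow was taken. The planned reporting does not call for separating SD that was checked in marrow from SD that was not.

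**Working it through.** **Step 1. Is a marrow required before SD?** Taking the passages together:

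- Appendix 10, SD: no marrow named.
- Section 7.4: marrow when clinically indicated, or to confirm a response.
- Section 7.1 tables, treatment cycles: marrow when clinically indicated.
- End-of-treatment marrow: optional. Crossover marrow: Arm A only, after progression.
- Exploratory marrow: asked of everyone in Section 7.6.1, but under footnote 17 taken only when a disease-assessment marrow is done or at crossover.

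None makes a post-baseline marrow a condition for SD.

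**Step 2. Who could be misclassified?** SD counts if reached at any time and needs more than 8 weeks without evidence of progression. Later marrow progression does not undo it. The exposed group is therefore subjects whose marrow blasts progress within about the first 8 weeks without a qualifying change in blood or transfusion need and without anything that prompts a marrow.

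**Step 3. Reproduce the design figures.** Inputs from Section 9.1.2: stop at or below 1/10, 2/12, 3/14, 3/16, 4/18, 5/20, 6/22, 8/24 and 9/26; success at 12 or more of 28. Let f_n(k) be the probability of k successes in n subjects without having stopped:

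f_n(k) = f_{n-1}(k)(1 − p) + f_{n-1}(k − 1)p,

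with f_n(k) set to 0 at each look when k is at or below the limit. The chance of claiming success is the sum of f_28(k) over k ≥ 12.

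- p = 0.30: 0.0991 (Section 9.2.1 states 0.099).
- p = 0.50: 0.8174 (Section 9.2.1 states 81%).
- The Table 5 continuation probabilities for n = 10 to 26 match to four decimals.

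The design arithmetic is correct.

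**Step 4. Illustrate the effect.** Suppose the true CBR is 0.30 and a share m of the arm has marrow-only progression scored SD. The observed success rate is then p = 0.30 + m. The expected number of misclassified subjects is 28m, and their share of true failures is m/0.70. The values of m are assumptions; the documents give none.

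| m (points) | p | 28m | m/0.70 | P(success), Table 5 limits applied | P(success), no interim looks |
|---|---|---|---|---|---|
| 0 | 0.30 | 0 | 0% | 0.099 | 0.103 |
| 3 | 0.33 | 0.84 | 4.3% | 0.175 | 0.181 |
| 5 | 0.35 | 1.4 | 7.1% | 0.240 | 0.247 |
| 10 | 0.40 | 2.8 | 14.3% | 0.438 | 0.449 |

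An average of one misclassified subject per arm (m = 1/28, about 3.6 points) gives 0.192 with the Table 5 limits, nearly double the stated value. Treating those limits as binding or as guidance makes little difference.

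**The case against.** The case on the other side has weight, and several parts of it stand.

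- **Some on-treatment marrow is foreseen.** Section 5.5.3 bases dose adjustment on marrow cellularity at the nadir for subjects with low baseline counts, once WBC or platelets fall by 50% or more. A reader might infer that SD is always assigned with no on-treatment marrow. The documents do not support that; what they lack is a requirement.
- **Blood tests catch much progression.** Appendix 10 has count-based, hemoglobin and transfusion rules, Table 4 includes a blast count, and CBCs are frequent in Cycles 1 and 2. These can show progression or prompt a marrow. This limits the size of the problem but does not close the gap for blast rises that stay silent in blood.
- **Section 7.4 may already cover SD.** Section 9.1.2 and Table 5 use the word response for SD, so confirming a response could include SD. Against that, ORR and duration of response exclude SD, and the schedules give only the clinical-indication condition. The text is ambiguous.
- **Error in the other direction is possible.** A reader might infer that omitted marrow can only inflate CBR. That is not shown for every path. A drug-related platelet fall (Section 2.2.4 reports a median nadir of 29 G/L at 2 mg) could meet a progression rule while the marrow is in remission. A marrow CR before 8 weeks could also go unrecorded in a subject who then stops.
- **The benchmark.** The protocol does not say how SD was ascertained for the 30% reference rate. Similar ascertainment there would offset some of the bias.
- **Reporting already planned.** ORR, which excludes SD, is reported by arm with exact intervals, and response types are summarized separately. This helps, but it does not separate SD with marrow from SD without.

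**Conclusion.** The point stands as a gap in endpoint ascertainment. SD is a primary success, blast progression is defined only in marrow, and no passage requires a post-baseline marrow before SD is assigned. Early blast progression that blood and transfusion data do not show would be scored SD, would not fall under the missing-response rule, and would add to the success count.

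The mechanism follows from the text; the size does not. The figures 0.175, 0.240 and 0.438 rest on assumed shares of 3, 5 and 10 points, a true CBR of 0.30, and no offsetting error in the other direction. A reader might infer that the real type I error is one of these values. The documents support only the statement that the stated 0.099 assumes no such misclassification, and that about one subject in 28 is enough to move it materially.

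A reader might also infer that an arm should be called active only if it passes with marrow-unsupported SD removed. That does not follow: with marrow unscheduled, such a gate could move the test towards ORR against a threshold set for CBR.

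**What to change.** 1. **Section 9.4.1.** Keep the primary 12-of-28 rule. Report the count behind it in three parts: CR, mCR, PR, cytogenetic response or HI; SD with a post-baseline marrow; SD without one. Add a supporting CBR in which SD without marrow is treated as unknown, and so as non-response under the existing rule. State in the conclusion whenever a success claim depends on SD without marrow. The cost is one more summary from data already collected. The supporting CBR is conservative and can only be equal or lower, and the stated 81% power does not apply to it.

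2. **Sections 7.4, 7.6.1 and 7.1 (footnotes 11 and 17).** Reconcile the request for on-study marrow from all subjects with the footnotes that make it conditional and allow the sponsor to end it. State whether confirming the response in Section 7.4 includes SD. This is a clarification and should add no marrow beyond what the protocol already requests. A newly mandated marrow would be an extra procedure and is not proposed here.

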7.5. Pharmacokinetics

7.5.1. Blood Sample Collection

Blood samples for pharmacokinetic (PK) analysis of GSK2879552, GSK2879552 metabolite(s), as deemed appropriate, and azacitidine will be collected at the time points indicated in the Time and Events Schedule (Section 7.1).

Each PK sample should be collected as close as possible to the planned time relative to the dose (i.e., time zero) administered to the subject on PK days. The actual date and time of each blood sample collection will be recorded along with the date and time of the prior dose administration. The timing of PK samples may be altered and/or PK samples may be obtained at additional time points to ensure thorough PK monitoring. This would not require a protocol amendment.

Details on PK blood sample collection, processing, storage and shipping procedures are provided in the SPM.

7.5.2. Sample Analysis

Plasma sample analysis will be performed under the control of Bioanalysis, Immunogenicity & Biomarkers (BIB), In Vitro/In Vivo Translation (IVIVT), Platform Technology and Science (PTS), GlaxoSmithKline. Concentrations of GSK2879552, GSK2879552 metabolite(s), as deemed appropriate, and azacitidine will be determined in plasma samples using the currently approved bioanalytical methodology. Raw data will be archived at the bioanalytical site. Once the plasma samples have been analysed for GSK2879552, any remaining plasma may be analysed for other compound-related metabolites and the results reported under a separate protocol.

